8.3.14 Medication Error, Drug Abuse, and Drug Misuse

8.3.14.1 Timelines

Medication error, Drug Abuse and Drug Misuse alone are not AE/SAE. All Medication Errors/Drug Abuse/Drug Misuse are to be collected for IMPs and provided to AstraZeneca DES via the respective Medication Error eCRF module or Drug Abuse/Drug Misuse paper CRF forms. If an AE/SAE is associated with the Medication Error/Drug Abuse/Drug Misuse, the AE/SAE eCRF modules should also be completed and sent to AstraZeneca DES.

If an event of medication error, drug abuse, or drug misuse occurs during the study, then the investigator or other site personnel informs the appropriate AstraZeneca representatives within **one calendar day**, ie, immediately but **no later than 24 hours** of when they become aware of it.

The designated AstraZeneca representative works with the investigator to ensure that all relevant information is completed within **one** (initial fatal/life-threatening or follow-up fatal/life-threatening) **or 5** (other serious initial and follow-up) **calendar days** if there is an SAE associated with the event of medication error, drug abuse, or misuse (see Section 8.3.12) and **within 30 days** for all other events.

8.3.14.2 Medication Error

For the purposes of this clinical study a medication error is an **unintended** failure or mistake in the treatment process for an IMP that either causes harm to the patient or has the potential to cause harm to the patient.

The definition of a medication error can be found in Appendix B 4.

8.3.14.3 Drug Abuse

Drug abuse is the persistent or sporadic **intentional**, non-therapeutic excessive use of IMP for a perceived reward or desired non-therapeutic effect.

The full definition and examples of drug abuse can be found in Appendix B 4.

8.3.14.4 Drug Misuse

Drug misuse is the **intentional** and inappropriate use (by a study patient) of IMP for medicinal purposes outside of the authorised product information, or for unauthorised IMPs, outside the

intended use as specified in the protocol and includes deliberate administration of the product by the wrong route.

The full definition and examples of drug misuse can be found in Appendix B 4.

8.4 Overdose

For this study, any dose of study treatment greater than those specified in the protocol is considered to be an overdose. There is currently no specific treatment in the event of overdose of durvalumab or ceralasertib, and possible symptoms of overdose are not established. This may include a higher dose of study treatment or study treatment taken at the correct dose but for longer duration.

Overdose alone is not an AE/SAE. All overdoses are collected for IMPs and provided to AstraZeneca DES:

- An overdose with associated AEs is recorded as the AE diagnosis/symptoms on the relevant AE modules in the eCRF and on the Overdose eCRF module.
- An overdose without associated symptoms is only reported on the Overdose eCRF module.

If an overdose on an AstraZeneca study treatment occurs in the course of the study, the investigator or other site personnel inform appropriate AstraZeneca representatives immediately, but **no later than 24 hours** of when he or she becomes aware of it.

The designated AstraZeneca representative works with the investigator to ensure that all relevant information is provided to the AstraZeneca Patient Safety data entry site within 1 or 5 calendar days for overdoses associated with an SAE (see Section 8.3.12) and within 30 days for all other overdoses.

8.5 Human Biological Samples

Instructions for the collection, storage, and shipping of biological samples will be provided in the study specific Laboratory Manual. Samples should be stored in a secure storage space with adequate measures to protect confidentiality.

Samples will be stored for a maximum of 15 years from the end of the study (last patient last visit) in line with consent and local requirements, after which they will be destroyed/repatriated.

• PK samples will be disposed of after the Bioanalytical Report finalisation or 6 months after issuance of the draft Bioanalytical Report (whichever is earlier), unless consented for future analyses.

- Pharmacokinetic samples may be disposed of or anonymised by pooling. Additional
 analyses may be conducted on the anonymised, pooled pharmacokinetic samples to
 further evaluate and validate the analytical method. Any results from such analyses
 may be reported separately from the CSR.
- Remaining sample aliquots will be retained at AstraZeneca or its designee for a maximum
 of 15 years from the end of the study (last patient last visit). Additional use includes but is
 not limited to further characterisation of any ADAs, confirmation and/or requalification
 of the assay as well as additional assay development work. The results from future
 analysis will not be reported in the CSR.

No personal details identifying the individual will be available to the sponsor or designated organisations working with the DNA.

The patient's consent to the use of donated biological samples is mandatory.

Biological samples (eg, archival tumour samples, on-study tumour samples, and blood) will be collected as detailed in the Laboratory Manual in order to carry out biomarker analysis to assess correlations with disease activity, effects of study drug, clinical outcomes and toxicity. The tumour specimens should be of sufficient quality and quantity to allow for next generation sequencing and other analyses to be carried out (see the Laboratory Manual).

The biomarker data may also be pooled with biomarker data from other studies to test existing hypotheses or to generate hypotheses to be tested in future studies with the agents studied.

For further details on Handling of Human Biological Samples see Appendix C.

8.5.1 Pharmacokinetics

- Venous blood samples for determination of concentrations of study treatment in plasma or serum will be taken at the times specified in the SoA (Section 1.3). The date and time of collection of each sample will be recorded.
- Samples may be collected at additional time points during the study if warranted and agreed upon between the investigator and the sponsor, eg, for safety reasons. The timing of sampling may be altered during the course of the study based on newly available data (eg, to obtain data closer to the time of peak or trough matrix concentrations) to ensure appropriate monitoring. The total volume of blood taken from each patient will not exceed that presented in Section 8.
- Plasma or serum blood samples will be used to analyse the PK of the study treatment. Samples collected for analyses of study treatment concentration may also be used to evaluate safety or efficacy aspects related to concerns arising during or after the study.

Samples will be collected, labelled, stored, and shipped as detailed in the Laboratory Manual.

8.5.1.1 Determination of Drug Concentration

Samples for determination of study treatment concentration in plasma or serum will be assayed by bioanalytical test sites operated by or on behalf of AstraZeneca, using an appropriately validated bioanalytical method. Full details of the analytical method used will be described in a separate bioanalytical report.

Incurred sample reproducibility analysis, if any, will be performed alongside the bioanalysis of the test samples. The results from the evaluation, if performed, will be reported in a separate Bioanalytical Report.

8.5.2 Immunogenicity Assessments

Blood samples for determination of ADA in serum/plasma will be assayed by bioanalytical test sites operated by or on behalf of the sponsor, using an appropriately validated bioanalytical method. Full details of the methods used will be described in a separate report.

ADA samples may also be further tested for characterisation of the ADA response.

Samples will be collected to evaluate immunogenicity to durvalumab as specified in the SoA. Evaluations will be performed using validated immunoassays. Tiered analyses will be performed to include screening, confirmatory, and titer assay components. Blood samples (~3.5 mL) will be collected at screening, then pre-dose on Day 1 of Cycles 1, 2, 3, and 4, then every 4 cycles, end of treatment, and 30 days after last dose for ceralasertib monotherapy and 30 days, 90 days and 6 months after last dose for ceralasertib and durvalumab combination.

Samples will be collected, labelled, stored, and shipped as detailed in the Laboratory Manual.

8.5.3 Pharmacodynamics

8.5.3.1 Collection of Samples

Blood and urine samples are mandatory and will be collected as per the timepoints detailed in the SoA (Section 1.3).

For storage, re-use and destruction of pharmacodynamic samples see Section 8.5 and Appendix C.

8.6 Human Biological Sample Biomarkers

8.6.1 Collection of Mandatory Samples for Biomarker Analysis

By consenting to participate in the main or biopsy sub-study the patient consents to participate in the mandatory research components of the study.

Tumour and blood samples for biomarker research are required and will be collected from all patients in this study as specified in the SoA (Section 1.3). Samples will be tested for primary, secondary and exploratory objectives, to understand potential candidate predictive biomarkers, pharmacodynamics and MoA of ceralasertib and ceralasertib plus durvalumab, early/late biomarkers of response, and potential resistance mechanisms. The samples may also be used for future diagnostic development

All patients (main study and biopsy sub-study) will be required to provide archival tumour samples (Section 8.6.1.1). The main study will require collection of tumour biopsies at screening, if medically feasible (Section 8.6.1.2). Biopsy sub-study will require collection of serial mandatory tumour biopsies.

Any sample material remaining after completion of analyses to fulfil the study objectives may be used to develop methods, assays, prognostics, and/or diagnostic tests related to cancer, disease process, pathways associated with disease state.

For further details on Handling of Human Biological Samples, including storage, re-use and destruction, refer to Section 8.5 and Appendix C.

8.6.1.1 Mandatory Archival Tumour Samples

Archival tumour tissue (FFPE blocks) obtained within 5 years prior to enrolment and associated pathology report(s) should be obtained at screening for all patients enrolled into the study. Archival tumour tissue must have been formalin fixed for 24 to 48 hours immediately after collection and then embedded in paraffin blocks. If FFPE blocks of archival tumour tissue obtained within 5 years prior to enrolment are not available, then unstained slides (a minimum of 20 freshly cut unstained sections, prepared less than 6 months prior to enrolment) from the relevant archival tumour tissue must be available.

8.6.1.2 Tumour Biopsies for Main and Biopsy Sub-Study

All patients must consent to the mandatory use of donated biological samples.

Details of the tumour biopsy collection for the main study and biopsy sub-study are mentioned below. The associated pathology report(s) for fresh tumour samples will be required at

screening and requested on-treatment for all patients enrolled into the study (details in the Laboratory Manual). Where clinically feasible, serial biopsies should be taken from the same lesion and when not feasible, serial biopsies should be taken from the same tissue. Biopsies should be completed with a minimum 18-gauge needle. Fine needle aspirates are not acceptable. Biopsies should not be obtained from bone metastasis. If clinically practical, subjects should undergo 4 core biopsies, but a minimum of at least 3 core biopsies are required. The first and third core biopsies will be placed in formalin and processed for FFPE, while the second and fourth core biopsies (4th biopsy, if available) will be immediately frozen in liquid nitrogen and then stored at -80°C.

Details for fresh tumour sample collection, processing, storage, and shipment are provided in the Laboratory Manual. Per institutional practice, image-guided fresh core needle tumour biopsies should be preferentially obtained from tumour tissues that are safely accessible, as determined by the investigator, and are not obtained from sites that require significant risk procedures. For fresh tumour biopsies, the tumour lesion should not be used as a RECIST target lesion, unless this is the only soft tissue lesion. If a RECIST 1.1 target lesion is used for biopsy, the lesion must be ≥ 2 cm in the longest diameter.

Tumour samples will be analysed for a number of biomarkers with potential association to response or resistance to treatment and/or with the MoA of ceralasertib as monotherapy or in combination with durvalumab. Biomarker may include, but not be limited to: mutations or polymorphisms in specific genes; tumour mutational burden; expression of genes or gene signatures; the number, phenotype, and expression profile of immune cells such as T-cells; the expression of one or more proteins; epigenetic or mutational profiles or signatures.

For main study, A fresh tumour biopsy sample will be collected at screening (Days -21 to -1) unless medically (or technically) not feasible. If a biopsy is not feasible, a tumour tissue sample collected within 5 years prior to enrolment must be provided. If a further tissue sample, independent of age, is available in addition to the mandatory pre-treatment sample, then this should also be provided.

For biopsy sub-study, all study patients are required to provide 3 mandatory fresh tumour biopsy samples for testing at:

- Screening (Days -21 to -1)
- On-ceralasertib treatment, Cycle 0 (on Day 7) of ceralasertib monotherapy, and
- Off-ceralasertib treatment, Cycle 0 (between Days 15 to 28).

Any additional tumour tissue (optional) available should also be submitted.

8.6.1.3 **Blood Samples for Exploratory Biomarker Assessments** 8.6.1.3.1 8.6.1.3.2 8.6.1.3.3 8.6.1.3.4 8.6.1.3.5 8.6.1.3.6

8.6.2 Collection of Optional Biomarker Samples
8.6.2 Collection of Optional Biomarker Samples
8.6.2.1 Optional Biopsies

8.6.3 Other Study Related Biomarker Research

CCI	
8.6.	4 Optional Future Scientific Research
CCI	
CCI	
8.7	CCI
CCI	
•	CCI
•	CCI
CCI	

See Appendix D for information regarding the Genomics Initiative genetic sample.

8.8 Health Economics OR Medical Resource Utilization and Health Economics

Medical Resource Utilisation and Health Economics parameters are not evaluated in this study. Health Economics/Medical Resource Utilisation and Health Economics parameters are not evaluated in this study.

9 STATISTICAL CONSIDERATIONS

9.1 Statistical Hypotheses

No formal statistical hypotheses are being conducted for this study.

9.2 Sample Size Determination

9.2.1 Main Study

Objective response rate is the primary endpoint in this study. The primary analysis will be conducted once all randomised patients have had a minimum of months of follow-up after start of study treatment or have discontinued from the study, whichever occurs first. It is anticipated that the median duration of follow up for DoR will be at least months at this point, however if not, then the primary analysis may be postponed to ensure a minimum of months median duration of follow up. At this primary analysis the CSR will be written.

It is anticipated at least approximately 60% of all randomised patients will have progressed or died at the time of the primary analysis. However, if this is not the case, a later analysis for PFS may be conducted once approximately 60% of all randomised patients have progressed or died.

A col analysis will be conducted once approximately 60% of all randomised patients have died, or 60 years from when the last patient starts treatment, whichever is earliest.

Each treatment arm is experimental and thus will be analysed separately for ORR. The study will recruit approximately 100 patients in the ceralasertib and durvalumab combination therapy arm. With 100 patients the expected width of the % CI for ORR will be up to approximately % when the proportion of patients with an objective response is in the range % to %. For example, ORR 601%, 601%, 601%. The study will recruit approximately 50 patients in the ceralasertib monotherapy arm. With 50 patients, the expected width of the % CI for ORR will be up to approximately % when the proportion of patients with an objective response is in the range % to %. For example, ORR 601%, 60%, 601%. The sample size of the ceralasertib monotherapy arm may be expanded up to a total of approximately 100 patients. This would occur in the event an efficacy signal is observed, and subject to a protocol amendment.

There is no standard of care after anti-PD-(L)1 immunotherapy for the intended patient population. Objective response rate for chemotherapy treatment options for patient second line and beyond, post-ipilimumab, are previously reported to be 4% (95% CI 2%, 9%) and 10% (95% CI 5%, 16%). There is no prospective clinical trial data on response rates for chemotherapy specifically in the post CPI-resistant setting. An ORR of % is considered an upper limit of expected response rate for alternative available treatment options for the intended patient population in this study. Per the proposed Phase 2 study design, with 100 evaluable patients in the ceralasertib and durvalumab combination therapy arm, success will be achieved if a minimum ORR of % is observed, for which the % exact CI would be (CCI %, CCI %).

A secondary objective is to compare the ORR between the two treatment arms. With 150 patients (100 patients randomised to ceralasertib and durvalumab combination therapy arm and 50 patients randomised to ceralasertib monotherapy), there will be at least \(\sigma\) power at a \(\sigma\) to detect a difference in ORR, assuming an ORR for ceralasertib plus durvalumab of \(\sigma\) and an ORR for ceralasertib monotherapy of \(\sigma\).

Enrolled	Estimated CCI patients
Randomly assigned	Estimated 150 patients
Evaluable patients	Estimated 150 patients

Note: "Enrolled" means a patient's, or their legally acceptable representative's, agreement to participate in a clinical study following completion of the informed consent process. Potential patients who are screened for the purpose of determining eligibility for the study, but are not randomly assigned/assigned in the study, are considered "screen failures", unless otherwise specified by the protocol. For country-specific requirements for Germany see Appendix K 1.3.

9.2.2 Biopsy Sub-Study

[figure not shown]
Approximately patients are planned to be enrolled such that approximately 30 patients have at least 2 evaluable paired biopsies (at the baseline and off ceralasertib treatment) including at least 15 patients with at least 3 evaluable biopsies (at baseline, on ceralasertib treatment and off ceralasertib treatment).

Sample sizing is based on expected fold increase in CD8+ T-cells infiltration. The fold assumption represents the observed increase in proliferating CD8+ T-cells infiltration in association with Pembrolizumab and Nivolumab or Nivolumab/Ipilimumab efficacy in melanoma (Tumeh et al, 2014; Grasso et al, 2020).

The sample size of 30 evaluable patients is expected to give adequate sample size to assess changes of CD8+ T-cells from baseline. With 30 evaluable patients and a standard deviation

of College -scale), the expected 60% CI for CD8+ T-cells fold change from baseline is presented in the table below for a range of example observed values.

Table 15 Expected W CI for CD8 T-cells Fold Change from Baseline with a Standard Deviation of Colom-scale) and 30 Evaluable Patients

The primary analysis for the biopsy sub-study will be conducted once all enrolled patients have had a minimum of months of follow-up after start of study treatment or have discontinued from the study, whichever occurs first. At this primary analysis the CSR for the biopsy sub-study will be written, which may be finalised after the CSR is finalised for the main study. A collapse analysis will be performed either months after the last patient is enrolled, or 60% of patients have died, whichever is the earlier event.

9.3 Populations for Analyses

The populations for analysis are listed in Table 16.

Table 16 Populations for Analysis

Population/Analysis set	Description	Endpoint/Output
Enrolled analysis set	All patients who sign the ICF.	Disposition
Safety analysis set	All patients receiving at least 1 dose of study treatment. Patients will be summarised according to the treatment received.	Baseline and demography Exposure Safety ORR BOR TTR DoR Tumour size PFS (biopsy sub-study only) OS (biopsy sub-study)

Population/Analysis set	Description	Endpoint/Output
Full analysis set (main study only)	All patients who are randomised in the study. The FAS will be used for all the efficacy analyses including PROs. Treatment groups will be compared on the basis of randomised study treatment, regardless of the treatment actually received. Patients who were randomised but did not subsequently receive study treatment are included in the analysis in the treatment group to which they were randomised.	Baseline and demography (supportive) ORR (for comparative analysis) PFS OS
PK analysis set	All dosed patients with reportable ceralasertib or durvalumab plasma concentrations. Patients will be summarised according to the treatment received.	PK concentrations
PD analysis set	All patients who receive at least 1 dose of study treatment with at least 1 reportable pharmacodynamic measurement.	PD endpoints
Interim response evaluable (main study only)	All dosed patients who have measurable disease at baseline by BICR and who have first dose at least prior to data cut off.	ORR (interim) BOR (interim) TTR (interim) DoR (interim) Tumour size (interim)

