- Arm 1: Ceralasertib 240 mg BD, oral tablets, from Days 1 to 7, plus durvalumab 1500 mg Day 8, IV infusion, Q28D, until progressive disease (confirmed RECIST 1.1-defined radiological progression), unacceptable toxicity, withdrawal of consent, or if a study treatment discontinuation criterion is met.
- **Arm 2:** Ceralasertib 240 mg BD, oral tablets, from Days 1 to 7, Q28D, until progressive disease (confirmed RECIST 1.1-defined radiological progression), unacceptable toxicity, withdrawal of consent, or if a study treatment discontinuation criterion is met.

There is no defined maximum treatment duration for the treatment arms as the patients will receive study treatment until progressive disease (confirmed RECIST 1.1-defined radiological progression), unacceptable toxicity, withdrawal of consent, or if a study treatment discontinuation criterion is met.

Randomization into the treatment arms will be stratified by:

- Resistance to prior immune-oncology treatment (primary/early relapse in adjuvant setting vs secondary resistance).
- Baseline lactate dehydrogenase expression (below and equal to the upper limit of normal vs above upper limit of normal).

Biopsy sub-study: During Cycle 0, patients will be treated with ceralasertib 240 mg BD, as oral tablets, from Days 1 to 7, Q28D, followed by an off-treatment period between Days 8 to 28. From Cycle 1, patients will be treated with the combination of ceralasertib 240 mg BD, oral tablets, from Days 1 to 7, plus durvalumab 1500 mg Day 8, as an IV infusion, Q28D, until progressive disease (confirmed RECIST 1.1-defined radiological progression), unacceptable toxicity, withdrawal of consent, or if a study treatment discontinuation criterion is met.

Follow-up of patients post discontinuation of study treatment for main and biopsy sub-study: After study treatment discontinuation, all patients will be followed up for safety assessments 30 days after their last dose of study treatment for ceralasertib monotherapy or 180 days after last dose of study treatment for ceralasertib and durvalumab combination (ie, the safety follow-up visit). All randomised patients in the main study and all patients in the biopsy sub-study will be followed for survival status and post discontinuation anti-cancer therapies. For country-specific requirements for Belgium and France see Appendices K 1.1 and K 1.2 respectively.

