3 OBJECTIVES AND ENDPOINTS

Table 5 Objectives and Endpoints for Main Study

Objectives	Endpoints
Primary	
To estimate the effectiveness of ceralasertib monotherapy and ceralasertib plus durvalumab by assessment of objective response rate (ORR) in patients with unresectable or advanced melanoma and primary or secondary resistance to a PD-(L)1 inhibitor	ORR is defined as the proportion of patients who have a confirmed complete response, (CR) or confirmed partial response (PR), as determined by Blinded Independent Central Review (BICR) per Response Evaluation Criteria in Solid Tumours (RECIST 1.1) The analysis will include all dosed patients as dosed. Data obtained from randomisation up until progression, or the last evaluable assessment in the absence of progression, will be included in the assessment of ORR, regardless of whether the patient withdraws from therapy. Patients who go off study treatment without a response or progression, receive a subsequent therapy, and then respond will not be included as responders in the ORR. The primary measure is the estimate of ORR for each experimental treatment arm, and a secondary measure of interest is the odds ratio of the ORR comparing the 2 treatment arms. Additionally, ORR will be analysed using the
	investigator assessment per RECIST 1.1 as a sensitivity analysis.
Secondary	
To estimate the effectiveness of ceralasertib monotherapy and ceralasertib plus durvalumab by assessment of Duration of Response (DoR) in patients with unresectable or advanced melanoma and primary or secondary resistance	DoR will be defined as the time from the date of first documented confirmed response until date of documented progression per RECIST 1.1 as assessed by BICR or death due to any cause The analysis will include all dosed patients as dosed
to a PD-(L)1 inhibitor	who have a confirmed response, regardless of whether the patient withdraws from study treatment, receives another anti-cancer therapy or clinically progresses prior to RECIST 1.1 progression.
	The measure of interest is the median and landmark estimates at 6, 9, 12, 15, and 18 months of DoR. Additionally, DoR will be analysed using the
	investigator assessment per RECIST 1.1 as a sensitivity analysis.

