4 STUDY DESIGN

4.1 Overall Design

Main study: This is a Phase 2, randomised, open-label, multicentre, international study assessing the efficacy and safety of ceralasertib and ceralasertib plus durvalumab in patients with unresectable or advanced melanoma and primary or secondary resistance to PD-(L)1 inhibition. Patients will be recruited from multiple centres with a global footprint that is expected to include North America, Europe, and Asia.

Approximately 150 patients will be randomised, at a 2:1 randomisation ratio (approximately 100 patients in Arm 1 and approximately 50 patients in Arm 2) to the following intervention groups:

- 1 **Arm 1:** Ceralasertib 240 mg BD Days 1 to 7 plus durvalumab 1500 mg Day 8, Q28D, until progressive disease, unacceptable toxicity, withdrawal of consent, or if a study treatment discontinuation criterion is met.
- 2 **Arm 2:** Ceralasertib 240 mg BD Days 1 to 7, Q28D, until progressive disease, unacceptable toxicity, withdrawal of consent, or if a study treatment discontinuation criterion is met.

Randomisation will be stratified by resistance to prior immune-oncology treatment and baseline LDH expression. At enrolment, investigators will confirm the PD-(L)1 resistance type and whether LDH is normal or above upper limit of normal in order to stratify the patients accordingly. For further details on randomization, refer to Section 6.3.1.

Crossover between treatment arms is not permitted.

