9.4.2.1.2 Objective Response Rate

Determination of ORR by BICR is the primary objective, and as a sensitivity analysis, ORR by investigator recorded assessments will also be evaluated. Objective response rate is defined

as the proportion of patients who have a CR or PR prior to any evidence of progression (as defined by RECIST 1.1) that is confirmed at least 4 weeks later. The primary analysis of objective response rate will be based upon the safety analysis set. A sensitivity analysis will also be provided in the subset of patients in the safety analysis set who also have measurable disease at baseline by BICR. Data obtained from randomisation up until progression, or the last evaluable assessment in the absence of progression, will be included in the assessment of ORR, regardless of whether the patient withdraws from therapy. Patients who discontinue treatment without a response or progression, receive a subsequent therapy, and then respond will not be included as responders in the ORR.

As primary analysis, ORR will be summarised for each treatment arm non-comparatively with 95% CI (Clopper-Pearson).

As a secondary objective, ORR will be compared between the treatment arms using logistic regression adjusting for PD-(L)1 resistance type and LDH per randomisation stratification as covariates. The results of the analysis will be presented in terms of an odds ratio for study treatments together with associated 95% profile likelihood CI and p-value (based on twice the change in in log-likelihood resulting from the addition of a treatment factor to the model). This comparative analysis will be provided using the full analysis set.

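### Grouping the primary ORR by treatment received would, read literally, count combination-arm patients who stop before their first durvalumab dose as monotherapy; the bias is one-directional but probably small

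*Protocol*

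**What the plan says.** Protocol section 9.4.2.1.2 fixes the set: "The primary analysis of objective response rate will be based upon the safety analysis set". Table 16 (section 9.3) defines that set as "All patients receiving at least 1 dose of study treatment. Patients will be summarised according to the treatment received" and lists ORR, BOR, TTR, DoR and tumour size against it. Table 5 (section 3) repeats the rule for ORR: "The analysis will include all dosed patients as dosed".

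Section 4.1 gives the regimens. Arm 1 is "Ceralasertib 240 mg BD Days 1 to 7 plus durvalumab 1500 mg Day 8, Q28D". Arm 2 is "Ceralasertib 240 mg BD Days 1 to 7, Q28D, until progressive disease". The two are identical through Day 7.

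The per-arm ORR is reported non-comparatively with an exact 95% interval. The odds ratio between arms is a secondary measure and uses the FAS, grouped as randomised; PFS and OS in the main study also use the FAS. Section 9.2.1 reads success from a minimum observed ORR in the combination arm; the threshold is redacted.

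The FAS row of Table 16 also states "The FAS will be used for all the efficacy analyses including PROs", although the same table puts the response endpoints under the safety set.

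**The concern.** The grouping rule makes membership of the combination group depend on an event after randomisation: receiving a first durvalumab dose. A monotherapy patient who stops on Day 5 stays in monotherapy. A combination patient who stops on Day 5 has received exactly the Arm 2 treatment and, on the plain wording, moves there. For early stoppers the transfer runs only one way.

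The patients moved are not typical. The first scheduled scan is at Week 8 (section 8.1.1), and a response must be confirmed at least 4 weeks later (section 9.4.2.1.2). Someone who dies, withdraws or stops permanently in the first week is very unlikely to become a confirmed responder. Moving them takes non-responders out of one denominator and adds them to the other.

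Two readings are exposed. One is the combination-arm ORR on which success is judged. The other is the monotherapy ORR, which section 4.2 wants in order to understand what ceralasertib contributes to the combination. The interim response evaluable set in Table 16 also takes dosed patients, states no grouping rule, and supports the arm-specific stopping guidance in section 9.5.

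**Working it through.** **The plan's own figures.** 150 patients at 2:1 gives 150 × 2/3 = 100 and 150 × 1/3 = 50, as stated. The interval widths, power, target ORRs and success threshold in section 9.2.1 are redacted and cannot be reproduced.

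**Inputs**
- Arm sizes: 100 and 50 (section 4.1).
- Combination responders: 30/100, an assumption matching the 30% ORR of the earlier combination study in melanoma (section 4.2).
- Monotherapy responders: 10/50, an assumption, with 5/50 as a variation.
- k, the number of combination patients given ceralasertib but never durvalumab: not in the protocol. It is varied, and all k are first taken as non-responders.

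**Formula.** As-dosed combination ORR = 30/(100 − k). As-dosed monotherapy ORR = 10/(50 + k). Grouping dosed patients by randomised arm is the case k = 0.

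| k | Combination (exact 95% CI) | Monotherapy (exact 95% CI) |
|---|---|---|
| 0 | 30/100 = 30.0% (21.2–40.0) | 10/50 = 20.0% (10.0–33.7) |
| 1 | 30/99 = 30.3% (21.5–40.4) | 10/51 = 19.6% (9.8–33.1) |
| 2 | 30/98 = 30.6% (21.7–40.7) | 10/52 = 19.2% (9.6–32.5) |
| 5 | 30/95 = 31.6% (22.4–41.9) | 10/55 = 18.2% (9.1–30.9) |

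Each moved patient adds about 0.3 points to the combination and takes about 0.4 from monotherapy. With 5/50 monotherapy responders the second figure is about 0.2 (5/50 = 10.0% against 5/51 = 9.8%).

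**Equal true rates.** From 20/100 and 10/50 (20% in both arms), k = 5 gives 20/95 = 21.1% and 10/55 = 18.2%. The gap comes from the grouping alone.

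**If some moved patients respond.** With k = 5 and r responders among them, the rates are (30 − r)/95 and (10 + r)/55. At r = 1 they are 30.5% and 20.0%; at r = 2 they are 29.5% and 21.8%. The direction therefore holds unless about 2 of 5 first-week stoppers go on to a confirmed response.

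**Success reading.** The threshold is redacted, so take two assumed bars. To put the exact 95% lower limit above 15%, 23 responders are needed out of 100 and 22 out of 95. To put it above 10%, 17 are needed in both cases. At k = 5 the grouping is worth at most one responder on these bars.

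**The case against.** The strongest reply is that no passage explicitly reclassifies these patients. The wording is general, section 9.4 says the SAP will be more technical and detailed, and the treatment of partial receipt of a two-drug regimen is often settled there. This limits the certainty, but it does not remove the point: the protocol itself fixes the as-dosed rule for its primary endpoint, and its plain meaning gives the biased grouping. The nearest protective rule, in section 9.4.3.1, assigns AEs after a dose modification to the initial dose group and covers AEs only.

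The second reply is that few patients would be affected, and this largely stands. Reclassification needs permanent cessation before any durvalumab. Interrupted ceralasertib may resume within its dosing window (section 6.2.2.2) and delayed durvalumab may be resumed (section 6.6). Entry requires ECOG 0 or 1 and a life expectancy of at least 3 months (section 5.1.1). Section 4.3.2 reports discontinuation for AEs in 3/65 on the 7-day schedule elsewhere, over all treatment, and none in the earlier melanoma study. Those figures cover AEs only and differently sequenced regimens, but they make k = 5 look like an upper range.

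A reader might also infer that the trial's treatment comparison is distorted, because the gap between the arm rates at k = 5 grows from 10.0 to 31.6 − 18.2 = 13.4 points. The documents do not support that: no as-dosed difference is planned, and the odds ratio, PFS and OS are as randomised. Nor do they support calling the safety tables wrong. Summarising safety by treatment received is conventional, and toxicity before any durvalumab is toxicity on ceralasertib alone.

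**Conclusion.** The point holds in a limited form. On the plain wording, the primary per-arm ORR conditions arm membership on a post-randomisation event, which biases combination ORR up and monotherapy ORR down. BOR and change in tumour size share the grouping. So do TTR and DoR, but they are computed among responders and do not move if the reclassified patients are all non-responders.

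The size is modest: about 0.3 points per patient in the combination arm and 0.2 to 0.4 in monotherapy. Even at k = 5 the 1.6-point rise is small beside an interval about 19 points wide (21.2% to 40.0%). This rests on the assumed response rates, an unknown k, first-week stoppers being non-responders, and a literal reading of the grouping rule. It is worth correcting because the bias has a known direction, touches the primary estimate and the success reading, and is easily removed.

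The FAS sentence in Table 16 is a separate wording conflict. A reader might take it to mean that the FAS is the intended set for the primary ORR. The output column of the same row limits FAS use for ORR to the comparative analysis, and the synopsis, Table 5 and section 9.4.2.1.2 all place the primary ORR in dosed patients. Moving the primary ORR to the FAS is therefore an option, not something the protocol already requires.

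**What to change.** For ORR, BOR, TTR, DoR and change in tumour size, including the interim response evaluable set, keep dosed patients but group them by randomised arm. State that a patient randomised to the combination who received only ceralasertib stays in the combination arm. Keep grouping by treatment received for safety outputs. Amend the FAS sentence in Table 16 so that it covers only the analyses listed in that row, and align Table 5 and section 9.4.2.1.2.

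The cost is a few sentences in the protocol, carried into the SAP, with no new data and no change to the sample size. The downside is that any combination patients who never received durvalumab count in that arm's denominator and slightly lower its ORR: in the k = 5 illustration, 30.0% is reported instead of 31.6%. The wording should be settled before any further unblinded analysis of response by arm.
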